11. IMAGING PROTOCOL

Full details on the imaging protocol are in the Image Acquisition Standards.

11.1. ¹⁸F-fluciclovine PET Scan Patient Preparation

Patients should be advised not to eat for at least 4 hours prior to administration of ¹⁸F-fluciclovine injection. Patients may have water or other clear fluids within this time window.

11.2. PET/CT Scanner

A dedicated hybrid PET scanner (e.g., PET/CT, PET/MRI) is mandatory. The selected PET scanner must be qualified by the study management team.

11.3. ¹⁸F-fluciclovine Injection Administration

See [Section 8.8](#) and the Pharmacy Manual for administration instructions.

11.4. ¹⁸F-fluciclovine PET Acquisition

For the dynamic PET acquisition, subjects will be imaged for approximately 30 minutes. For the CT acquisition (if acquired on a PET/CT scanner), an unenhanced (no IV contrast) CT will be employed.

11.5. On-Study MRI Acquisition

All subjects will receive an on-study, study-specific brain MRI scan at Visit 2 consisting of standard MRI sequences including (1) T₁-weighted MRI without and with contrast enhancement, (2) FLAIR and/or T₂-weighted MRI, and (3) diffusion-weighted imaging, ideally on the same day as the PET scan or up to a maximum of 3 days after the PET scan.

A final on-study MRI will be performed at Visit 5 (Month 6) only for any surviving subject whose reference or other equivocal lesion(s) remain equivocal at site level, unless an SoC MRI was performed within the preceding 3 weeks.

11.6. Image Transfer

Following the completion of PET and on-study MRI imaging at the study site, the scan data will be sent to the Imaging Core Lab using either the Imaging Management Solution software or on physical media by courier.

11.7. Image Evaluability

Both PET and on-study MRI scans will be assessed by the Imaging Core Lab for evaluability based on the Image Quality Standards. All data will undergo quality control including technical analysis, indication and protocol specific criteria, based on the parameters detailed in the Image Acquisition Standards.

11.8. Central Evaluations

11.8.1. Central Histopathology

As described in [Section 10.5](#), a representative set of specimens obtained in subjects undergoing Visit 4 (SoC biopsy/neurosurgical intervention) will be shipped to a central

laboratory. This is to allow for central histopathology review. Detailed specification of this workflow, and assignment of recurrent metastasis (positive) vs no recurrent metastasis (negative) based on the central review, will be laid out prospectively in a histopathology charter.

11.8.2. Central Truth Panel

An independent panel consisting of an experienced neuro-oncologist, neuroradiologist, neuropathologist, neurosurgeon, and radiation oncologist with expertise in treating brain tumors will serve as a Central Truth Panel.

- The panel will establish a charter to prospectively define objective data review parameters including pre-specified MRI evaluation criteria.
- The panel will review the central histopathology results (where applicable) and clinical data (including site histopathology reports, follow-up MRI scans, and cancer-related therapies) to confer a diagnosis of recurrent metastasis (positive) vs no recurrent metastasis (negative) for each reference lesion, other equivocal lesion(s), and additional PET lesions.
- The clinical data will encompass a 6-month period following ¹⁸F-fluciclovine PET, or up to the time when the subject dies, whichever comes first.
- The Central Truth Panel will have no access to the ¹⁸F-fluciclovine PET scans, nor the study record of lesion diagnosis reached by the site.

11.8.3. Blinded Image Evaluation

A 3-reader central, independent BIE of the ¹⁸F-fluciclovine PET scans will be performed, diagnosing recurrent metastasis (positive) vs no recurrent metastasis (negative) for each reference lesion, other equivocal lesion(s) and additional PET lesion(s), using the Visit 2 MRI for anatomical reference.

- Image criteria used in the BIE will be informed by a Phase 2b study (BED-FLC-219).
- Inter- and intra-reader concordance will be measured.
- The readers will not have access to clinical history, prior clinical imaging, any site-generated diagnostic evidence, nor the final patient outcome.

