The site investigator will review the ¹⁸F-fluciclovine PET scan to identify potential additional lesions, not previously reported on SoC MRI (termed ‘additional PET lesions’). Additional PET lesions should be annotated only where judged suggestive of brain metastasis, warranting confirmation by clinical follow-up, biopsy or resection, according to SoC practice. Moreover, an additional PET lesion should be discrete and spatially separate from known, pre-existing lesions. In particular, the following should not be annotated as Additional PET lesions: known pre-existing non-progressive lesions (considered at site level as stable or partially responding), ¹⁸F-fluciclovine activity contiguous with a known lesion (previously annotated or otherwise) and apparently incongruent with the lesion’s outline on correlating MRI, particularly where this may be reasonably explained by image registration.

The investigator will then annotate the additional PET lesions on the ¹⁸F-fluciclovine PET scan using the imaging core lab study imaging platform. The site investigator will also confirm the sites of the reference and other equivocal lesions on the Visit 2 scans.

For each annotated lesion, a lesion identifier will be automatically created and assigned by the imaging core lab study imaging platform. For each annotated lesion, the site will also be required to define the anatomical location.

Subjects whose reference or other equivocal lesion(s) continue to be considered at the site-level to be equivocal for brain metastasis at Month 6 (Visit 5) will have a final research MRI unless an SoC MRI was performed within the prior 3 weeks.

9.1.5.1. ¹⁸F-fluciclovine PET Scan

Dynamic PET/CT or PET/MRI scan of the brain to be performed at Visit 2 following ¹⁸F-fluciclovine injection. If the PET scan is performed on a PET/CT scanner, a CT scan of the brain will also be performed for attenuation correction. Site investigator will review the ¹⁸F-fluciclovine PET scan to identify potential additional PET lesions (this will be done with the Visit 2 MRI scan for anatomical reference). The PET scan will be uploaded to the central imaging core laboratory by the site investigator/site staff. The selected PET scanner must be qualified by the study management team prior to any imaging studies. Full details on the imaging protocol are provided in the Imaging Acquisition Standards.

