15.6.5. Inter-Reader / Intra-Reader Agreement

Cohen's kappa statistic will be calculated to assess inter-reader and intra-reader agreement on ¹⁸F-fluciclovine PET scan central reads. The statistic will be presented for each pairwise comparison of the 3 readers for the inter-reader agreements, at the subject-level (i.e., reference lesion only) and also at lesion-level (i.e., all lesions defined by site). Similar statistics will be presented for the initial read vs re-read of a subset of PET scans for each reader.

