Subjects with additional metastases identified on ^{18}F -fluciclovine PET but not on SoC MRI are those with at least one lesion with type = 'Additional PET Lesion' on the lesion annotation eCRF page, which has SoR = 'positive' according to the CTP. Lesions that are deemed to have SoR = 'indeterminate' by CTP will not be considered as additional metastases.

The estimate of the proportion of subjects and the associated 95% 2-sided exact confidence interval (Clopper-Pearson) will be presented.

7.4.4.4.3 Proportion of subjects whose prospective diagnostic management plan changes following ^{18}F -fluciclovine PET.

The proportion of subjects whose prospective diagnostic management plan changes following ^{18}F -fluciclovine PET will be established by comparing the diagnostic management plan of the reference lesion before and after ^{18}F -fluciclovine PET.

The intended diagnostic management plan on the reference lesion will be recorded at visit 1 as craniotomy, biopsy, biopsy in context of LITT, or clinical follow-up. At visit 2, post ^{18}F -fluciclovine PET, the diagnostic plan will be recorded again. If a different option has been chosen, or if there are any additional/new subject management activities planned then this will be counted as a change.

The estimate of the proportion of subjects and the associated 95% 2-sided exact confidence interval (Clopper-Pearson) will be presented.

7.4.4.5 *Inter-Reader / Intra-Reader Agreement (Blinded Image Evaluation)*

For inter-reader agreement, pairwise comparisons of the ¹⁸F-fluciclovine PET scan central reads for the 3 readers (i.e. Reader 1 vs Reader 2, Reader 1 vs Reader 3, and Reader 2 vs Reader 3) will be performed at the subject-level (i.e., reference lesion only) and also at the lesion-level (i.e., all lesions defined by site). The number and percentage of each combination of results (Positive [1st reader] / Positive [2nd reader], Positive/Negative, Negative/Positive, Negative/Negative) will be presented, along with the number and percentage of results in agreement and disagreement. Cohen's kappa statistic will be calculated and presented for each pairwise comparison of the 3 readers, with the corresponding 95% CI and p-value.

Similar statistics will be presented for intra-reader agreement (10% of subjects) – comparisons will be between the initial read vs re-read of a subset of PET scans for each reader.

7.4.4.6 *Sensitivity Analyses*

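### Blinded readers must classify site-marked additional PET lesions, which can disclose a positive site PET read, and lesion-level results pool these lesions with MRI-selected ones

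*Protocol*

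**What the plan says.** Protocol 11.8.3 sets up a central blinded evaluation by three independent readers. It limits what they may know: "The readers will not have access to clinical history, prior clinical imaging, any site-generated diagnostic evidence, nor the final patient outcome". It also lists what they must call positive or negative: "each reference lesion, other equivocal lesion(s) and additional PET lesion(s), using the Visit 2 MRI for anatomical reference".

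Protocol 9.1.5 explains how the last type of lesion arises. The site investigator reviews the study PET for foci not already reported on the standard-of-care MRI, and marks them on the PET in the core laboratory's platform. The condition is: "Additional PET lesions should be annotated only where judged suggestive of brain metastasis, warranting confirmation by clinical follow-up, biopsy or resection". Protocol 4.1 and 10.3 and SAP 6.1 repeat it. The reference and other equivocal lesions are instead annotated on the standard-of-care MRI at Screening (Protocol 9.1.5 and 10.1), before the PET.

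The primary endpoint uses the reference lesion only (Protocol 15.5, SAP 7.4.3). Inter-reader kappa is computed, in Protocol 15.6.5, "at the subject-level (i.e., reference lesion only) and also at lesion-level (i.e., all lesions defined by site"). SAP 7.4.4.5 uses the same set, "also at the lesion-level (i.e., all lesions defined by site"). Lesion-level PPA, NPA, PPV and NPV also cover all three lesion types (Protocol 15.6.2, SAP 7.4.4.2). None of these analyses is split by lesion type.

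**The concern.** An additional PET lesion mark is the site's own positive reading of the same scan that the central readers are asked to judge independently. Protocol 11.8.3 withholds site diagnostic evidence, yet it asks for a call on an object that exists only because of such evidence. Neither document says what the readers see on screen or in what order they read.

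Two things are at stake. First, a reader who sees that the site found extra suggestive uptake elsewhere in the brain may carry that into the call on the reference lesion, which is the primary read. Second, the lesion-level results mix lesions chosen because MRI was equivocal with lesions chosen because a PET read was already positive. Agreement and accuracy in that mixture do not describe the equivocal-MRI lesions alone.

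**Working it through.** **1. Can the mark inform the reader?** Readers must classify every additional PET lesion, so they must be directed to it. Protocol 9.1.5 says the platform assigns each annotated lesion an identifier. It does not say whether readers also see the lesion type. Even a neutral identifier may not hide it. Reference and other equivocal lesions must meet inclusion criterion 7 (at least 5 mm on contrast-enhanced MRI, plus a growth or reappearance criterion). A marked focus with little to match it on the Visit 2 MRI is therefore likely to be recognised as PET-derived.

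**2. Can it reach the primary read?** Not through the reference lesion's own mark, which is made on MRI before the PET. It can do so only if a reader sees a mark on a separate lesion before calling the reference lesion. Nothing in 11.8.3 prevents this. The documents give neither the share of subjects with such a mark nor its effect on a reader, so no size can be derived.

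**3. What does pooling do to kappa?** The documents state no expected kappa, no kappa threshold and no number of additional PET lesions, so there is no stated figure to reproduce. The inputs below are assumptions.

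Base case: 150 MRI-selected lesions, with reader-by-reader counts (++, +−, −+, −−) of 60, 15, 15, 60. Kappa = (po − pe)/(1 − pe). Here po = 120/150 = 0.800 and pe = (75² + 75²)/150² = 0.500, so kappa = 0.600.

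| Lesions added | Table | po | pe | Kappa |
|---|---|---|---|---|
| 10, both readers positive | 70/15/15/60 | 0.8125 | 0.5020 | 0.624 |
| 20, both readers positive | 80/15/15/60 | 0.8235 | 0.5069 | 0.642 |
| 30, both readers positive | 90/15/15/60 | 0.8333 | 0.5139 | 0.657 |
| 20, each positive independently at 90% | 76.2/16.8/16.8/60.2 | 0.8024 | 0.5044 | 0.601 |
| 20, each positive independently at 80% | 72.8/18.2/18.2/60.8 | 0.7859 | 0.5025 | 0.570 |

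For the last two rows, 20 lesions at rate q add 20q² to ++, 20q(1 − q) to each discordant cell and 20(1 − q)² to −−.

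**4. Sensitivity to the base case.** With 130 base lesions, half called positive and kappa 0.60, adding 5, 10, 20 or 40 both-positive lesions gives 0.614, 0.627, 0.647 or 0.676. With 20 both-positive lesions, the result is 0.695 if 30% of base lesions are called positive and 0.622 if 70% are. With base kappa 0.80, half called positive and 20 added lesions, the result is 0.824 if all are both-positive, 0.776 at 90% independent and 0.740 at 80% independent.

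**5. Lesion-level performance.** An additional lesion that a central reader also calls positive can only be a true or a false positive, never a false or true negative. Such lesions push PPA up where the reference standard is positive and NPA down where it is negative. The size again depends on counts the documents do not give.

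**The case against.** A reader might infer that the blinded read is unmasked as a whole, so that the primary endpoint is biased. The documents do not support that. The reference lesion is fixed on MRI before the PET, additional PET lesions must be spatially separate from known lesions, and subject-level endpoints and subject-level kappa use the reference lesion alone. The readers also see the PET itself, so much of any cue from extra uptake is legitimate image content. A push towards positive calls would lower NPA while raising PPA, and success requires both goals to be met by the same two readers, so the effect would not plainly favour the product. What stands is that no reading order is stated, which leaves the route open.

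A reader might also infer that lesion-level kappa is necessarily inflated. It is not: the increase requires near-uniform positive calls on the added lesions, and with some independent disagreement kappa stays flat or falls. Kappa is also a descriptive secondary measure with no success threshold, the lesion set is openly defined, and subject-level kappa is planned beside it.

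Finally, site diagnostic evidence can be read as meaning site reports and diagnoses rather than location marks, and a location is needed to match a read to the reference standard. That is a fair reading of the intent. It does not remove the information that the mark carries.

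**Conclusion.** The point holds as an internal inconsistency in Protocol 11.8.3 and an unseparated mixture in the lesion-level analyses. Being directed to an additional PET lesion can tell a blinded reader that the site read that focus as suggestive. The consequence for the primary read is a possible risk of unknown size, not a demonstrated bias. For lesion-level kappa, pooling can move an assumed 0.60 up to 0.62–0.66, leave it at 0.60, or lower it to 0.57, under the assumptions of the 150-lesion illustration. Direction and size depend on how many such lesions there are and how readers call them, and the documents give neither. Whichever way it moves, the pooled figure does not isolate performance on MRI-equivocal lesions.

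**What to change.** In Protocol 11.8.3 and the charter for the blinded evaluation, state what readers see and in what order. They read and lock the reference and other equivocal lesions with no additional PET lesion marks displayed. The additional lesions are then shown in a second step under neutral identifiers. If an operating document already sequences the reads this way, a cross-reference in 11.8.3 is enough for this part.

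In the Protocol synopsis, 15.6.2 and 15.6.5, and in SAP 7.4.4.2 and 7.4.4.5, report lesion-level kappa and lesion-level PPA, NPA, PPV and NPV both with and without additional PET lesions. Changing both documents together avoids a Protocol–SAP mismatch and keeps the lesion sets for agreement and accuracy aligned.

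The cost is a reading-platform setting, wording changes, a slightly longer reading session and a few extra table rows. No new subjects, images or readers are needed.

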11.8.4. Central Neuroradiologist Reader

A neuroradiologist reader will independently review the reference lesion on the historical and Screening SoC MRI scans to assess each subject's baseline equivocal status. This independent determination will be applied to a sensitivity analysis of the primary endpoint.

12. ADVERSE EVENT REPORTING AND DOCUMENTATION

12.1. Adverse Events

An AE is any untoward medical occurrence in a clinical investigation subject administered a pharmaceutical product and that does not necessarily have a causal relationship with the treatment. An AE is therefore any unfavorable and unintended sign (including an abnormal laboratory finding), symptom or disease temporally associated with the administration of an investigational product, whether or not related to that investigational product. An unexpected AE is one of a type not identified in nature, severity, or frequency in the current Investigator's Brochure or is of greater severity or frequency than expected based on the information in the Investigator's Brochure.

The investigator will probe, via discussion with the subject, for the occurrence of AEs during each subject visit within the AE collection period. The collection period for all AEs will begin after initiation of ¹⁸F-fluciclovine injection and end 1 day post ¹⁸F-fluciclovine administration (i.e., Day 2). Any unresolved AE at Visit 3 Safety Follow-up beyond Day 2 will be followed until resolution or stabilization. The investigator will record the information in the site's source documents. Adverse events will be recorded in the subject electronic Case Report form (eCRF). Adverse events will be described by duration (start and stop dates and times), severity, outcome, treatment and relation to study drug.

12.2. AE Severity

The National Cancer Institute's Common Terminology Criteria for Adverse Events (CTCAE) Version 5 (November 27, 2017) will be used to assess and grade event severity, including laboratory abnormalities judged to be clinically significant. For events not specifically mentioned in CTCAE, the general severity grading is provided below ([Table 2](#)).

Table 2. CTCAE (V5) AE Severity Grading

Severity (Toxicity Grade)	Description
Grade 1	Mild; asymptomatic or mild symptoms; clinical or diagnostic observations only; intervention not indicated.
Grade 2	Moderate; minimal, local or non-invasive intervention indicated; limiting age-appropriate instrumental ADL.*
Grade 3	Severe or medically significant but not immediately life-threatening; hospitalization or prolongation of hospitalization indicated; disabling; limiting self-care ADL**.
Grade 4	Life-threatening consequences; urgent intervention indicated.
Grade 5	Death related to AE.

ADL, activities of daily living; AE, adverse event; CTCAE, Common Terminology Criteria for Adverse Events.

*Instrumental ADL refer to preparing meals, shopping for groceries or clothes, using the telephone, managing money, etc.

** Self-care ADL refer to bathing, dressing and undressing, feeding self, using the toilet, taking medications, and not bedridden.

12.3. Adverse Event Relationship to IMP

The relationship of an AE to IMP will be categorized as follows:

Related: when there is a reasonable possibility of a causal relationship between IMP administration and an AE (i.e., adverse drug reaction).

Not related: when an AE does not follow a reasonable temporal sequence from IMP administration or when an AE can be reasonably explained by other factors including underlying disease, concomitant drugs or concurrent treatment.

12.4. Serious Adverse Event (SAE)

An SAE is defined as any adverse event occurring at any dose that results in any of the following outcomes:

- death
- a life-threatening adverse experience
- inpatient hospitalization or prolongation of existing hospitalization
- a persistent or significant disability/incapacity
- a congenital anomaly/birth defect

Other important medical events may also be considered an SAE when, based on appropriate medical judgment, they jeopardize the subject or require intervention to prevent one of the outcomes listed above.

12.4.1. Serious Adverse Event Reporting

Study sites will document all SAEs that occur (whether or not related to study drug) on an SAE Report Form. The collection period for all SAEs will begin after initiation of ¹⁸F-fluciclovine injection and end 1 day post ¹⁸F-fluciclovine administration (i.e., Day 2). After this point, the investigator is not required to actively solicit SAE information from subjects. However, if they should become aware of an SAE that they suspect is related to the IMP, then they should report it. Any unresolved SAE beyond Day 2 at Visit 3 Safety Follow-up phone call, will be followed until resolution or stabilization.

All SAEs must be reported within 24 hours of the site study team becoming aware of the event by sending the completed SAE Report Form by fax, or scanned and emailed, to:

Bracco Diagnostics Inc. Drug Safety Unit:
[contact]
[contact]

Additional and further requested information (follow-up or corrections to the original event) will be detailed on a new SAE Report Form and faxed/mailed to the same address.

For the US, in accordance with the standard operating procedures and policies of the local Institutional Review Board (IRB)/Independent Ethics Committee (IEC) the site investigator will report SAEs to the IRB/IEC.

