4. STUDY DESIGN

4.1. Study Overview

This is a prospective, open label, single arm, single dose study in subjects with solid tumor brain metastases previously treated with radiation therapy, designed to establish the diagnostic performance of ¹⁸F-fluciclovine PET (read with standard MRI for anatomical reference) in detecting recurrent brain metastases where MRI is equivocal.

Subjects with a history of brain metastases previously treated with primary, adjuvant or repeat (salvage) radiation therapy, with a recent SoC brain MRI found to be equivocal for recurrent brain metastasis, and who meet all inclusion criteria and none of the exclusion criteria, will be consented and enrolled. The study population will be balanced to represent different primary tumor types of any origin, with a minimum of approximately 15% of the cohort each with lung cancer, breast cancer and melanoma. The number of subjects with lung cancer will be capped at approximately 50% of enrolled subjects.

Investigator will prepare a diagnostic management plan prior to the ¹⁸F-fluciclovine PET scan and will update the plan following the scan. All eligible subjects will receive an ¹⁸F-fluciclovine PET scan (Visit 2 PET) within 42 days of SoC MRI. Subjects will then undergo a repeat study-specific brain MRI scan (Visit 2 On-Study MRI) to be used for anatomical reference, ideally on the same day, otherwise ≤ 3 days after Visit 2 PET and completed before any pre-planned neurosurgical intervention when applicable. A Safety Follow-up (Visit 3) 1 to 3 days after IMP injection/PET (Visit 2 PET) will be made for AE evaluation by telephone call or in person (if same day as other scheduled SoC appointments). AEs occurring from the time of ¹⁸F-fluciclovine administration until 1 day post-¹⁸F-fluciclovine administration will be recorded. The Safety Follow-up must be completed before the pre-planned SoC biopsy/neurosurgical intervention, if applicable. Subjects who experience an SAE or an AE that persists at Visit 3, will be followed until resolution or stabilization of these events. All ongoing follow-up and any further treatment will be in accordance with SoC.

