6.3. Exclusion Criteria

1. Pregnant or breastfeeding during participation in the study, or, where applicable, unwilling to abstain from sexual conduct for 24 hours post-¹⁸F-fluciclovine injection.
2. Subjects with any medical condition or circumstance that the investigator believes may confound the data collected.
3. Subjects with active hematological malignancy or cancer of unknown primary.
4. Subject has received, or is scheduled to receive, another IMP from 1 month or within 5 half-lives of the other IMP (whichever is shorter) before ¹⁸F-fluciclovine injection to the completion of Visit 3.*

**Subjects receiving concurrent systemic therapies, including immunotherapies, are permitted for study entry as long as the concurrent therapy is not an IMP.*

5. Known contraindications to a contrast-enhanced MRI procedure.

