9. STUDY PROCEDURES AND GUIDELINES

A schedule of events representing the required study procedures to be performed for the duration of the study is provided in [Table 1](#).

Prior to conducting any study-related activities, written informed consent (and assent, if applicable) including Health Insurance Portability and Accountability Act (HIPAA) authorization must be signed and dated by the subject or LAR ([Section 17.3](#)).

Table 1. Schedule of Study Procedures

	Day -42 to -1 SoC MRI	Visit 1 Day -28 to -1 Screening	Visit 2 Day 1 IMP + PET	Visit 2 Day 1 to 4 On-Study MRI	Visit 3 Day 2 to 4 Safety Follow-Up Phone Call	Visit 4 Day 2 to 22 SoC Biopsy / Neurosurgical Intervention (if applicable)	Visit 5 Month 6 (183 days ± 14 days) Follow-up
SoC MRI					1 to 3 days after ¹⁸ F-fluciclovine injection, before optional SoC Biopsy / Neurosurgical Intervention (if applicable)	If applicable, at time of pre-planned SoC Biopsy / Neurosurgical Intervention and after Visit 2 MRI and Visit 3 Follow-Up	Through 6 months after ¹⁸ F-fluciclovine PET
Before Visit 1 Screening		Within 28 to 1 day before Visit 2 Day 1	Within 28 to 1 day before Visit 2 Day 1	Neurosurgical Intervention Visit 4 Day 3			
Informed Consent	X						
Confirm inclusion/exclusion criteria		X		X			
Demographics ^a	X						
Baseline Characteristics ^b				X			
Medical / Disease History ^c				X			
ECOG Performance Status ^d				X			
Concomitant Medications				X		X	
Vital Signs ^e				X		X	
Pregnancy Test (Urine) ^f				X		X	
Diagnostic Management Plan				X		X	
Order ¹⁸ F-fluciclovine dose				X			
Eligibility Review ^g				X			
¹⁸ F-fluciclovine Injection					X		
Dynamic PET Brain Scan					X		
Adverse Events					X		
On-Study MRI Brain Scan					X		X ^h
Annotate Reference Lesion on SoC MRI Brain Scan				X			
Annotate other equivocal lesions (if applicable) ⁱ				X			

Table 1. Schedule of Study Procedures

	Day -42 to -1 SoC MRI	Visit 1 Day -28 to -1 Screening	Visit 2 Day 1 IMP + PET	Visit 2 Day 1 to 4 On-Study MRI	Visit 3 Day 2 to 4 Safety Follow-Up Phone Call	Visit 4 Day 2 to 22 SoC Biopsy / Neurosurgical Intervention (if applicable)	Visit 5 Month 6 (183 days ± 14 days) Follow-up

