10.4. Visit 3 – Safety Follow-up (+1 to 3 days after IMP Injection/PET)

1. Clinical safety review by telephone call (or in person if same day as scheduled SoC biopsy, Visit 2 MRI, or other planned visit) to assess concomitant medications and AEs.
2. Record any changes in concomitant medications since Screening (Visit 1).
3. Record any AEs which have occurred during the safety reporting period (from the time of ¹⁸F-fluciclovine administration until 1 day post ¹⁸F-fluciclovine administration). For scheduling purposes, the subject may be contacted up to 3 days after IMP injection, but the assessment is to be limited to the first day after IMP injection only.

10.5. Visit 4 – SoC Biopsy/Neurosurgical Intervention (if applicable, pre-planned 1 to 21 days after IMP Injection/PET)

Where this visit is applicable, SoC biopsy/neurosurgical intervention should also take place after both the Visit 2 on-study MRI brain scan and Visit 3 Safety Follow-up.

1. Document neurosurgical procedure:
 - a. Record sites of reference lesion and other equivocal lesions which underwent SoC biopsy, and where applicable, ‘additional PET lesion(s)’, if performed.
 - b. Record sites of reference lesion and other equivocal lesions which underwent resection, and where applicable, ‘additional PET lesion(s)’, if performed.*
- c. If applicable, record neuronavigation system used for neurosurgical procedure.

* *Undertaking biopsy/resection of additional PET lesion(s) identified on the ¹⁸F-fluciclovine PET scan is at the discretion of the on-site investigators. The lesions should be judged suggestive of brain metastasis, warranting confirmation according to SoC practice. The subject will receive post-procedural management per institutional SoC.*

- d. Where biopsy was performed, upload image/screenshot of neuronavigation system depicting stereotactic coordinates of biopsy. Where resection was performed, upload image/screenshot of neuronavigation system depicting the surgical resection plan/approach (if neuronavigation was not used for resection, a representative screenshot of the post-procedure MRI demonstrating the resection cavity is suitable).
- e. Upload neurosurgical procedural report.
- f. Record any clinical factors associated with the neurosurgical intervention which impacted the type of procedure performed.

2. Label specimens with lesion ID as referenced by the imaging core laboratory study imaging platform on the previously annotated scans.

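### A non-fatal reaction to a study-mandated MRI on Day 3 or 4, or at Month 6, has no required route into the study's safety data

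*Protocol*

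**What the plan says.** **The MRI.** Protocol 4.1 states: "Subjects will then undergo a repeat study-specific brain MRI scan". Sections 9.1.5.2 and 11.5 specify T1-weighted imaging with and without contrast, and 11.5 sets the timing: "ideally on the same day as the PET scan or up to a maximum of 3 days after the PET scan". Table 1 in Section 9 heads the column "Visit 2 Day 1 to 4 On-Study MRI". At Month 6, a subject whose reference or other equivocal lesion is still equivocal at the site "will have a final research MRI unless an SoC MRI was performed within the prior 3 weeks" (9.1.5, repeated in 10.6). Section 6.3 excludes subjects with the following: "Known contraindications to a contrast-enhanced MRI procedure".

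**Safety collection.** Under 12.1 and 12.4.1, AEs and SAEs of any cause are collected from the start of the injection to Day 2. Visit 3 may take place on Day 2 to 4, but under 10.4 "the assessment is to be limited to the first day after IMP injection only". For SAEs after Day 2, 12.4.1 says "After this point, the investigator is not required to actively solicit SAE information from subjects" and asks only for those suspected to be related to the IMP. Section 12.3 opens its causality scale with "The relationship of an AE to IMP will be categorized as follows" and offers two categories, related and not related. SAP 6.4.2.1 and 7.5.2 keep the same one-day window.

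**Deaths.** Date and cause of death are collected to Month 6 (Protocol 10.6) and listed (SAP 7.5.3).

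**The concern.** The study imposes two separate exposures: the tracer, and a contrast MRI done because the study needs it. The safety rules are built around the first. Their window is counted from the injection and their causality scale refers only to the IMP, whereas the MRI can fall after that window has closed. Exclusion criterion 5 shows that the protocol knows contrast MRI is unsuitable for some people. The risk section (2.1.2) nevertheless discusses the intravenous injection and radiation and does not mention MRI contrast.

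What is at stake is whether harm from a study-imposed procedure reaches the sponsor's database. The diagnostic-performance result does not depend on it.

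**Working it through.** The documents state no figure to reproduce. The check sets the permitted MRI days against the collection days, with the injection on Day 1.

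1. Permitted Visit 2 MRI days: 0 to 3 days after PET, that is Day 1 to Day 1 + 3 = Day 4 (11.5 and Table 1). There are four permitted days.
2. End of AE and SAE collection: Day 1 + 1 = Day 2 (12.1, 12.4.1).
3. Month 6 window: 183 − 14 = 169 to 183 + 14 = 197 days (10.6).

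| MRI day | Inside any-cause AE/SAE collection? | Rule for a non-fatal reaction attributed to the MRI |
|---|---|---|
| Day 1 (preferred) | Yes | Recorded; reported within 24 hours if serious |
| Day 2 | Yes, for onset on Day 2 | Same |
| Day 3 | No | None if non-serious; if serious, asked for only when the IMP is suspected |
| Day 4 | No | Same as Day 3 |
| Month 6 (169 to 197 days) | No | Same as Day 3 |

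So 2 of 4 permitted Visit 2 days, and the whole Month 6 window, lie outside collection.

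Four other provisions might have closed the gap:

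- **Visit 3.** It may be made in person on the day of the Visit 2 MRI (10.4), so staff can be with the subject on Day 3 or 4. The AE assessment is still limited to the first day after injection. The contact can also be made on Day 2, before a later MRI.
- **Visit 5.** This is mainly a record review without the subject present. Its listed items are diagnoses, imaging, treatments, neurological deterioration and mortality, not AEs (10.6).
- **The general duty to report all SAEs.** Protocol 17.6, item 8, gives way where the protocol specifies otherwise, and 12.4.1 does so.
- **The SAP listing.** SAP 7.5.2 lists all AEs, including those that are not treatment-emergent, but it can show only what the protocol collects.

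None of the four requires a Day 3, Day 4 or Month 6 MRI reaction to be recorded as an AE.

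**The case against.** The strongest reply is that the window suits the stated aim. The safety objective concerns the tracer, a single dose with a half-life of about 110 minutes (8.3), and no attributable SAE had been reported (1.1). Contrast MRI is also routine in this population, since each subject needed such a scan within 42 days before PET to enter. This justifies the IMP window, and the fix leaves that window alone. It does not justify having no rule for a second exposure that the study itself adds.

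There are partial backstops. Visit 3 records changes in concomitant medication, sites report SAEs to their IRB/IEC under local policy, and the reason for a withdrawal enters the eCRF. These may leave a trace of some reactions, but they do not put the event into the study's AE data.

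Three stronger readings are tempting, and the documents do not support them:

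- *That MRI reactions in general go unrecorded.* Within the window AEs are collected whatever their cause, the preferred MRI day is Day 1, and AEs unresolved at Visit 3 are followed to resolution or stabilization.
- *That contrast reactions distort the tracer's safety tables.* An all-cause TEAE table is meant to include them. The not-related category in 12.3 accommodates events explained by other factors, and SAP 7.5.2 tabulates IMP-related events separately.
- *That every subject faces an uncovered Month 6 contrast scan.* That scan is only for surviving subjects who are still equivocal, and it is waived after a recent SoC MRI. Contrast is specified for the Visit 2 scan; at Month 6 it is only implied by calling the scan an on-study MRI.

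**Conclusion.** The point holds in a limited form. A non-fatal reaction attributed to a study-mandated MRI on Day 3 or 4, or at Month 6, falls outside the stated recording rules. The gap comes from what the rules say, not from a missing detail: 12.4.1 limits later reports to suspected IMP-related SAEs, and 10.4 limits the Visit 3 assessment.

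Its size can be stated only in days: 2 of 4 permitted Visit 2 MRI days, plus all Month 6 research MRIs. This is not half of the subjects, because Day 1 is preferred. The documents give neither the spread of MRI days nor a reaction rate. The number of Visit 2 scans outside the window could be anything from none to all of those done, and the number of missed reactions cannot be estimated.

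The conclusion assumes that sites apply the sections as written and that no manual outside these documents adds procedure-related reporting. The primary endpoint, power and IMP-related safety tables do not change. It is a low-cost improvement in safety recording.

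**What to change.** - **Protocol 10.4, 12.1 and 12.4.1:** keep the IMP and TEAE window as it is. Add that any AE or SAE suspected to be related to a study-mandated MRI or its contrast is recorded whatever the study day and, if serious, reported within the existing 24-hour timeline.
- **Protocol 12.3 and the eCRF:** add a field for relationship to a study procedure, with the procedure specified.
- **SAP 7.5.2:** list these events separately from the TEAE and IMP-related summaries.

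The cost is a protocol amendment, one eCRF field, one SAP output and a few more event reports. No visit is added.
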